## 12. Progress of the Research

**To meet federal requirements the IRB is relying on your RESEARCH DESCRIPTION as a protocol summary and their expectation is that it is up-to-date.** If the currently approved protocol (or research description) in your E-IRB application is outdated, please make applicable changes, and describe in the field below any substantive changes and explain why they are essential. If none, insert "N/A" in the text field below. If you are closing your study, you may use the space below to summarize the final status of the research.

We have stopped recruitment because of COVID-19 and are waiting for this pandemic to subside before recruiting additional patients.

Note: No changes in the research procedures should have occurred without previous IRB review. Approval from the IRB must be obtained before implementing any changes.

Provide a brief **summary** of any **modifications that affect subject safety and/or welfare** approved by the IRB since the last initial or continuation review (If none, insert "N/A" in the text field below.):

No new modifications.

Attach one copy of the most recent progress report sent to the FDA, if available. All PI-sponsored IND/IDE studies are required to submit a copy of the FDA progress report.

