**Short Title Description**

Note: "Short Title" should consist of a couple key words to easily identify your study - these key words (rather than the whole title) will be displayed on the Dashboard in the listing for your study.

Effects of All-Stim 2 Quadriceps  
Treatments on Lim

Anticipated Ending Date of Research Project: [i](#) 12/30/2021

Number of human subjects (or records/specimens reviewed) [i](#) 24

Study is/will be open to new subject enrollment or data/specimen collection: [i](#)  Yes  No

**PI CONTACT INFORMATION****0 unresolved  
comment(s)**

The Principal Investigator's (PI) contact information is filled in automatically based on who was logged in when the application was created (with LinkBlue ID). If research is being submitted to or supported by an extramural funding agency such as NIH, a private foundation or a pharmaceutical/manufacturing company, the PI listed on the grant application or the drug protocol must be the same person listed below.

If you are not the Principal Investigator, do NOT add yourself as study personnel. You may change the PI contact information on an application that is in Researcher edit mode by:

- clicking the "Change Principal Investigator" link below;
- searching for the PI's name using the search feature;
- clicking "Select" by the name of the Principal Investigator, then "Save Contact Information".

You will automatically be added as study personnel with edit authorization so you can continue editing the application.

Please fill in any blank fields with the appropriate contact information (gray shaded fields are not editable). Required fields left blank will be highlighted in pink after you click "Save".

To change home and work addresses, go to [myUK](#) and update using the Employee Self Service (ESS) portal. If name has changed, the individual with the name change will need to submit a '[Name Change Form](#)' to the Human Resources Benefits Office for entering into SAP. The new name will need to be associated with the individual's Link Blue ID in SAP before the change is reflected in E-IRB. Contact the [HR Benefits Office](#) for additional information.

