**Introduction**

I should point out that we are requesting a renewal for a previously approved protocol. We have recruited 15 patients to date and plan to finish this study by the end of the next review cycle. All the following information was included in the original Form B of the approved protocol.

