*Research Repositories:* If the purpose of this submission is to establish a Research Repository (bank, registry) indicate whether the material you plan to collect would or would not be available from a commercial supplier, clinical lab, or established IRB approved research repository. Provide scientific justification for establishment of an additional repository collecting duplicate material. Describe the repository design and operating procedures. For relevant information to include, see the UK Research Biospecimen Bank Guidance [\[PDF\]](#) or the UK Research Registry Guidance [\[PDF\]](#)

The basic study design is to:

- (a) obtain informed consent;
- (b) measure magnetic stimulated quadriceps twitch (QuadTw) strength bilaterally;
- (c) randomize patients to treatment with either:

Sham therapy, consisting of bilateral placement of All-Stim 2 electrodes for 30 minutes a day without activation of the electrical circuitry of the unit, or

Active therapy, using the All-Stim 2 electrodes to actively produce a rhythmic quadriceps contraction for 30 minutes a day.

We plan to have a total of 24 patients in the study, with two patients randomized to active treatment for every one patient given sham treatment. As a result we anticipate the final group studied will include 14-16 active treatment patients and 6-8 sham treatment patients.

- (d) continue these regimens daily for 7 days;
- (e) remeasure magnetic stimulated QuadTw on day 8;
- (f) the research team will visit the patient until discharge and will record duration of mechanical ventilation, duration of ICU stay, and total duration of hospitalization; and,
- (g) patients will be visited by a member of the research team at 28 days after study entry to assess the distance that can be walked in 6 minutes (i.e. the 6 minute walk test) and to assess patient well being using the St. Georges Research Questionnaire (SGRQ, a commonly used and extensively validated instrument to assess patient well being).

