Inclusion into the study will be considered for all adult patients requiring mechanical ventilation for more than 48 hours for respiratory failure in one of the University of Kentucky adult ICU's. We will include patients regardless of gender, race, or adult age. It is hoped that sufficient minorities and women will be studied so that the subject population is representative of the general patient population, but we will be somewhat constrained by the numbers of available patients and the day to day makeup of the patient population in the UK ICU's. Inclusion of minorities and women will make the study results more generally applicable.

Patients will be excluded:

- (a) if the physician caring for the patient determines that the patient is too unstable to tolerate these measurements,
- (b) if the patient requires high dose pressors (more than 15 mcg/min of norepinephrine or more than 15 mg/kg/min of dopamine),
- (c) if the patient requires more than 80% FiO2 or more than 15 cm H2O of PEEP,
- (d) if the patient has a cardiac pacemaker or implanted defibrillator,
- (e) if the patient has received neuromuscular blocking agents within the 48 hours preceding testing,
- (f) if the patient has a history of a preexisting neuromuscular disease,
- (h) if the patient has profound and uncorrectable hypokalemia (less than 2.5) or hypophosphatemia (less than 1.0)
- (i) if the patient is a pregnant female,
- (j) if the patient is a prisoner,
- (k) if the patient is institutionalized,
- (l) if it is thought that the patient is terminal and will have care withdrawn within 7 days.

Our goal is to recruit 24 total patients into the study. We plan to study an additional 12 patients over the next 12 month period (1 patient/month).

Attachments

**Subject Recruitment Methods & Privacy:** Using active voice, describe plans for the identification and recruitment of subjects, including how the population will be identified, and how initial contact will be made with potential subjects by those having legitimate access to the subjects' identity and the subjects' information.

Describe the setting in which an individual will be interacting with an investigator or how and where members of the research team will meet potential participants. If applicable, describe proposed outreach programs for recruiting women, minorities, or disparate populations as participants in clinical research. Describe steps taken to minimize undue influence in recruiting potential participants.

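### Does the forecast of 12 more patients, with 15 of 24 already enrolled, mean the trial will overshoot its planned size?

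*Combined protocol and SAP*

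**What the plan says.** The planned size is stated consistently. Study Design says "We plan to have a total of 24 patients in the study", with two patients allocated to active treatment for each one given sham, and adds that "we anticipate the final group studied will include 14-16 active treatment patients and 6-8 sham treatment patients". Study Population says "Our goal is to recruit 24 total patients into the study". Project Information enters 24 against "Number of human subjects (or records/specimens reviewed"), and item 5 of the continuation review (Subject Info To-Date) records 24 as the approved estimate.

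Enrolment so far is also consistent. The Introduction to the Research Description says "We have recruited 15 patients to date and plan to finish this study by the end of the next review cycle", and item 5 gives a cumulative total of 15.

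The sentence that does not fit comes directly after the goal of 24 in Study Population: "We plan to study an additional 12 patients over the next 12 month period (1 patient/month").

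Two further statements bear on how to read it. The Introduction says of the text that follows it: "All the following information was included in the original Form B of the approved protocol". Item 12 (Progress of the Research) reports: "We have stopped recruitment because of COVID-19 and are waiting for this pandemic to subside before recruiting additional patients".

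**The concern.** Read together, the two Study Population sentences and the enrolment count cannot all be right. If 15 patients are in and 12 more are to come, the trial ends with 27, not 24. In a small trial with 2:1 allocation and few sham patients, an unexplained drift in the final number deserves a question. It could mean an undeclared increase in size, an unstated allowance for dropouts or replacements, or enrolment beyond the approved number. It could also leave the trial without a clear end to recruitment.

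**Working it through.** **Planned total**
- Approved estimate (item 5, Subject Info To-Date): 24.
- Project Information: 24.
- Planned-enrolment table by sex and ethnic origin: 1 + 1 + 7 + 15 = 24.
- Study Design: 24. The anticipated arm sizes sum to between 14 + 6 = 20 and 16 + 8 = 24, so their upper end is also 24. Exact 2:1 allocation of 24 gives 16 and 8, which are the upper ends of the two ranges.
- Study Population: 24.

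**Enrolled to date**
- Item 5: 15 previously reported + 0 new = 15.
- Item 14 (Subject Demographics): 4 men + 11 women = 15.
- Introduction: 15.

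**Check of the forecast**
- Places remaining: 24 - 15 = 9.
- Enrolled plus forecast: 15 + 12 = 27. Excess: 27 - 24 = 3, and 3/24 = 12.5%.
- Enrolment at which the forecast reaches 24: 24 - 12 = 12. The sentence therefore agrees with the stated goal only if 12 patients had been enrolled when it was written.
- Time at the stated rate: 9 patients at 1 per month is 9 months, against the 12 months forecast.

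**Could the 12 be deliberate?** An enrolment of 27 would leave 24 evaluable patients if the loss were 1 - 24/27 = 11.1%. No dropout allowance or replacement rule is stated. The anticipated final group of 20 to 24 suggests that losses are expected to come out of the 24, not to be added to it.

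**Does anything depend on the 12?** No power calculation or analysis threshold uses it. The Statistical Analysis Plan specifies t tests with Tukey post-hoc comparisons at 0.05 and does not refer to the number still to be recruited. The Data and Safety Monitoring section ties stopping to safety, with reviews every twelve months, not to an enrolment count. The 2:1 allocation is defined without reference to it.

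**The case for a change.** The best case for acting is that this is current text, not a change log. Item 12 of the form says that the review board relies on the Research Description as the protocol summary and expects it to be up to date. The sentence is the only place that gives a recruitment rate and a number still to be enrolled, and this section of the form asks for enrolment dates. A leftover figure explains the conflict but does not remove it, and correcting it would cost one sentence.

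Much of that stands. The number is out of step with the count of 15, and nothing in the documents reconciles them. That the figure was carried over from an earlier form is an inference: the Introduction points to an original form that is attached but not reproduced, so the origin of the 12 cannot be settled.

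The step from a stale forecast to a trial of 27 does not stand. Taking the 12 literally means overriding the goal in the sentence before it and four other statements of 24. A single forecast of pace does not outweigh a total given five times. The safeguards against drift are also in the form. Item 5 sets cumulative enrolment beside the approved estimate and asks for that estimate to be updated if it is exceeded, and item 12 requires approval before any change is put into effect. With recruitment stopped, the twelve-month timetable was not running in any case.

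**Conclusion.** The discrepancy is real but clerical: a forecast of 12 where the stated total and the current count leave 9, a difference of three patients. The planned size of 24 is not in doubt, and a reader who meets both figures would sensibly take the 24 as governing. The forecast time is longer than 9 patients would need at the stated rate, so at that rate the error does not make the timetable look easier than it is.

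No change to the plan follows, because replacing the number would alter no target, allocation, analysis, safety measure or conclusion. This rests on two assumptions: that 24 is the intended total, which five separate entries support, and that no undisclosed replacement policy lies behind the 12, for which the documents give no sign. If the investigator did intend 27, that would be a different matter, and the form's own rules would require the approved number to be amended first.

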#### *Informed Consent for Research Involving Emancipated Individuals*

If you plan to enroll some or all prospective subjects as emancipated, consult with UK legal counsel **when preparing the IRB application and prior to submitting the application to the IRB**. Include legal counsel's recommendations (legal counsel's recommendations may be attached in the E-IRB "Additional Information" section as a separate document, if necessary). For a complete definition of emancipated minors, see the section on *Emancipated Individuals* in the Informed Consent SOP [\[PDF\]](#).

#### *Informed Consent for Research Involving Non-English Speaking Subjects*

If you are recruiting non-English speaking subjects, the method by which consent is obtained should be in language in which the subject is proficient. Describe the process for obtaining informed consent from prospective subjects in their respective language (or the legally authorized representative's respective language). In order to ensure that individuals are appropriately informed about the study when English is their second-language, describe a plan for evaluating the level of English comprehension, and the threshold for providing a translation, or explain why an evaluation would not be necessary. For additional information on inclusion of non-English speaking subjects, or subjects from a foreign culture, see [IRB Application Instructions for Recruiting Non-English Speaking Participants or Participants from a Foreign Culture](#).

#### *Research Repositories*

If the purpose of this submission is to establish a research repository describe the informed consent process. For guidance regarding consent issues, process approaches, and sample language see the Sample Repository/Registry/Bank Consent Template [\[PDF\]](#)

After reviewing the study with the patient and their family, the PI and/or [name] will ask the patient and the family if they wish to participate. The consent form will be reviewed with the patient and their family detailing the risks associated with the planned measurements. If the patient and family agree, the consent form will be signed. If the patient and their family wish they can think about the study and the PI will return the next day. After the consent form is signed, QuadTw measurements will be performed the same day and All-Stim 2 therapy will be started. The PI ([name]) or [name] will obtain all informed consents for the study. To eliminate coercion, all families and study recipients will be told that refusal to participate will in no way influence their care while at the University of Kentucky. Consent will be documented by having both the patient and the next of kin sign the consent form. Because most ICU patients receive some form of sedation, it is the intent of the PI to always inform the family as well as the patient and always have the family member with decision making power over the patient's care (e.g. their spouse or family member with power of attorney) sign the consent form. We will always seek to have the patients also sign the consent form. Under certain circumstances the patient may be so disabled that signage of the consent form is not possible (e.g. the patient is sedated or both hands are instrumented with IV's and pressure transducers). In the event of mental or physical inability of the patient to sign the consent form, the next of kin alone will sign the form.

[Back to Top](#)

**Research Procedures:** Describe the research procedures that will be followed. Identify all procedures that will be carried out with each group of subjects. Differentiate between procedures that involve standard/routine clinical care and those that will be performed specifically for this research project.

It will first be verified that the patient does not meet any exclusion criteria and that informed consent has been obtained.

**Quadriceps Twitch:** For this assessment, we will place a quadriceps board (Bailey Manufacturing) under the leg, positioned so that the knee lies immediately over the apex of the apparatus. We will then strap a force transducer (Interface, Model SSM-AJ) over the lower leg, positioned at one-fourth the distance between the lateral malleolus of the ankle and the knee. We will first assess twitch force with the apparatus set at the fourth "peg" position, corresponding to a 90o angle between the thigh and lower leg (we have found this corresponds to the optimal angle for quadriceps force generation in the majority of subjects). We will then adjust magnetic field strength during femoral nerve stimulation to ensure optimization of twitch force (i.e. usually at 85% of the maximum Magstim magnetic field strength). Five consecutive twitches will be performed at this setting. Subsequently, to verify the 90o knee angulation setting represents the optimal preload, twitches will be repeated at knee angle settings above and below 90o (i.e. at "peg" settings of 2 and 6). The average of the three best twitch forces generated at the optimal knee angle with supramaximal field strength will be averaged and this measure will be reported as the quadriceps twitch force. The technique will be repeated using the other leg. These measurements should take approximately 20 minutes.

**All Stim 2:** This device consists of a central controller which is attached to four soft adhesive electrodes. Two adhesive electrodes are placed over the quadriceps on each leg (two electrodes on the right, two electrodes on the left for a total of four electrodes). Once these electrodes are positioned, the controller is turned on and a stimulation regimen is selected. We will use a program in

which 45 Hz frequency current is used, with an on duration of 1 second and an off duration of 3 seconds; current intensity will be increased until the force generated by the quadriceps is 60% of the force generated by the quadriceps in response to magnetic twitch stimulation during the prior preliminary strength testing. (We have performed preliminary tests in normal individuals indicating that this level of force activation is well tolerated and produces a demonstrable reproducible submaximal quadriceps contraction). Once this current intensity is identified, all subsequent training trials will use this level of current density for training studies. Sham training will be performed with a setting of zero current intensity. Stimulation will be carried out as a single session per day with each session lasting 30 minutes.

**Initial Clinical Parameters:** These parameters will be obtained from the medical record using values collected as closely as possible to the time at which initial QuadTw physiological data measurements are made. Parameters will include age, sex, diagnoses, medications, reason for institution of mechanical ventilation, vital signs at the time of the initial visit, bedside parameters of mechanical ventilation use (including mode of ventilation, duration of ventilation, level of oxygen, breath volume and rate, % triggered breaths), most recent arterial blood gas values, and chest radiograph readings. To provide an assessment of pre-hospital function, family members will be asked four questions: (a) how far could the patient ambulate, (b) how many flights of steps could the patient go up, (c) which activities of daily living (dressing, carrying objects, performing daily grooming tasks), if any, were impaired, and (d) did the patient have difficulty standing from a sitting position or lifting objects over their head.

**Hospital Outcomes:** After recruitment into studies, electronic hospital records will be reviewed twice a week to determine the time from the point of initial study measurements to successful weaning from mechanical ventilation (defined as remaining off all mechanical ventilation for more than 4 days). Alternative outcomes that will be recorded, for patients that are not weaned from mechanical ventilation, include transfer to a chronic facility for long term weaning from mechanical ventilation (i.e. an LTAC) or death. Deaths will be further subclassified as death due to withdrawal of care and death due to progression of disease. We will also record total ICU stay, total days of hospital stay, and incidence of recurrent respiratory failure, defined as a requirement for reintubation either during the initial hospitalization or at any time out to day 28 after entry into the study. We will also record hospital readmission rates.

**Follow-up Visit (28 days).** At follow-up visits we will assess the distance walked in 6 minutes and we will ask patients if they have returned to work (either full time or part time). We will also have patients fill out the St. Georges respiratory questionnaire (SGRQ) on return visits. This questionnaire evaluates patient's perceptions about their respiratory health, including their assessment of the ability to perform simple tasks of daily living. The PI and/or [name] will visit the patient's domicile (or other site of habitation) to obtain these assessments.

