*Return of Research Results or Incidental Findings (if applicable):*

If research has the potential to identify individual results or discover incidental findings that could affect the health of a subject, describe plans to assess, manage, and if applicable disclose findings with individual subjects or provide justification for not disclosing. For IRB expectations, refer to the UK IRB "Frequently Asked Questions (FAQs) on the Return of Research Results or Incidental Research Findings" [[PDF](#)].

All data collected from the study (i.e. tracings of force measurements, demographic/clinical data obtained from chart review,) will be placed in a folder which will be stored in a locked filing cabinet in the office of the principal investigator in MN616. None of this information will be shared with other investigators. All folders will be given a study number and further analysis of mean data obtained from patient study folders will be carried out with only the patient study number as identification. Folders containing mean data will also be stored in the locked filing cabinet in MN616.

**Confidentiality:** Specify where the data and/or specimens will be stored and how the researcher will ensure the privacy and confidentiality of both. Please address the following items or indicate if the following has been addressed in a HIPAA or Limited Review form:

- physical security measures (e.g., locked facility, limited access);
- data security (e.g., password-protection, data encryption);
- who will have access to the data/specimens and identifiers;
- safeguards to protect identifiable research information (e.g., coding, links, certificate of confidentiality);
- procedures employed when sharing material or data, (e.g., honest broker if applicable, written agreement with recipient not to re-identify, measures to ensure that subject identifiers are not shared with recipients).
- management after the study

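### No masking is stated for the day-8 twitch measurement or the day-28 walk, and the twitch count and knee angle are only partly fixed, so the sham alone cannot rule out assessment bias

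*Combined protocol and SAP*

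**What the plan says.** **Measurement.** Research Procedures, Quadriceps Twitch, begins at a 90-degree knee angle. Field strength comes first: "We will then adjust magnetic field strength during femoral nerve stimulation to ensure optimization of twitch force". Then: "Five consecutive twitches will be performed at this setting". To check that 90 degrees is the best preload, "twitches will be repeated at knee angle settings above and below 90o", with no number given. The result is then defined: "The average of the three best twitch forces generated at the optimal knee angle with supramaximal field strength will be averaged". The section does not say whether tuning twitches can count, whether the angle is chosen afresh on day 8, who selects the three, or whether a twitch may be rejected.

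**Order.** Study Design lists baseline QuadTw as step (b), randomization as step (c) and the repeat on day 8 as step (e).

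**Sham.** Research Procedures, All Stim 2: "Sham training will be performed with a setting of zero current intensity". In the active arm the current is raised to a target force and the muscle contracts. Potential Risks adds that active stimulation tingles.

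**Day 28.** Under Follow-up Visit, the PI and/or one colleague "will visit the patient's domicile (or other site of habitation) to obtain these assessments". Study Design says only that a research team member visits.

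**Masking.** The form's Study Design prompt asks whether the trial is single or double blind. The answer describes sham and randomization and is silent on blinding. The nearest provision is in Research Materials, Records and Privacy: "further analysis of mean data obtained from patient study folders will be carried out with only the patient study number as identification". That covers later analysis, not acquisition or selection of twitches.

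**The concern.** A sham protects an outcome from assessment bias only if the assessor does not know which treatment was given. Here the person at the controller sets either zero current or a current that makes the thigh contract, so that person knows the arm. If that person, or anyone told by them, measures day-8 QuadTw, several choices that affect the result are open: how far to tune the field, how many twitches to take away from 90 degrees, and which angle to call optimal. The mean of the highest three rises with the number of tries and with the freedom to choose among angles.

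Equal selection in both arms cancels. Unequal selection on day 8 does not. Because baseline is taken before the arm is known, a day-8 imbalance passes straight into the change score and would look like a strength gain. The 6-minute walk has a parallel weakness, since encouragement by an assessor who knows the arm can affect effort.

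**Working it through.** **The plan's own figure.** At 2:1, 24 patients give 24 × 2/3 = 16 active and 24 × 1/3 = 8 sham, the upper ends of the stated 14-16 and 6-8. The total of 24 cannot be reproduced, because no effect size or power is given.

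**Inputs from the documents**
- Quadriceps twitch in ventilated patients: 12 with spread 4 N (Background). The 4 is not labelled; it is taken as an SD.
- Five twitches at 90 degrees, best three averaged, three angles tested (Quadriceps Twitch).
- Significance at 0.05 (Statistical Analysis Plan), taken as two-sided.

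**Assumptions, not in the documents**
- Within-session twitch SD of 5-15% of 12 N, that is 0.6-1.8 N.
- Independent normal twitches, three equally good angles, five twitches at each.
- A between-arm comparison at day 8; the SAP describes only before-after t tests.
- Free angle choice used in every active patient and in no sham patient.

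**Step 1: selection effect, in within-session SDs (simulation, 400,000 draws)**
- Mean of the best three of five at one pre-set angle: +0.555.
- The same, taking whichever of three angles gives the highest result: +0.973.
- Difference: 0.973 − 0.555 = 0.418.

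**Step 2: false gain in newtons**
- 5%: 0.418 × 0.6 = 0.25 N
- 10%: 0.418 × 1.2 = 0.50 N
- 15%: 0.418 × 1.8 = 0.75 N

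**Step 3: standard error of the arm difference**
- Unadjusted: 4 × √(1/16 + 1/8) = 1.73 N, 22 df.
- Adjusted for baseline with assumed r = 0.7: 1.73 × √(1 − 0.49) = 1.24 N, 21 df.

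**Step 4: type I error**, from the noncentral t distribution with noncentrality = false gain / SE

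| False gain | SE 1.73 N | SE 1.24 N |
|---|---|---|
| 0.25 N | 5.2% | 5.4% |
| 0.50 N | 5.9% | 6.7% |
| 0.75 N | 7.0% | 8.9% |

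**Step 5: with the procedure fixed.** Five twitches at one pre-set angle in both arms give +0.555 SD in each. The term drops out of the arm difference and the type I error stays at 5%.

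No size can be put on the walk test, because the documents give no figures for it.

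**The case against.** The strongest reply is that the measurement is already well constrained. QuadTw is evoked by nerve stimulation, so patient effort is removed. Five twitches are fixed at the angle said to be optimal in most subjects. The other two settings serve to verify that angle, and only supramaximal twitches at the chosen angle count. Best-of-three cancels when applied alike. The illustration loads all the freedom onto one arm, which nothing in the documents suggests. All of this stands and keeps the effect small. It does not supply a masked operator or selector, or a day-8 rule for the angle.

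A reader might infer more than the text supports:

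- **That the number of twitches is unlimited, or that 15 can be pooled across three angles.** Best three of 15 would give +1.31 SD, a false gain up to 1.4 N and type I error of about 19% at the smaller SE. But the three must come from one angle, so these figures do not follow from the rule.
- **That the same unmasked people treat, measure and follow up.** The documents do not say who stimulates, who measures QuadTw or who selects twitches. Names and personnel pages are removed, and the placeholders may be different people. Masking is unstated, not denied.
- **That the sham protects nothing.** It equalizes electrode placement and contact time. Ventilation and length-of-stay outcomes come from records and are much less exposed. The St. George's questionnaire is completed by the patient, so the risk there is the patient's own expectation. Walk distance is read from a pedometer (Potential Risks), which leaves encouragement as the main route.

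**Conclusion.** The point holds as a gap in the written procedure. With no masking stated and the angle choice open on day 8, the sham by itself cannot prevent assessment bias in day-8 QuadTw and the 6-minute walk. The plausible size for QuadTw is modest: a false gain of 0.25-0.75 N against a mean of 12 N, and type I error of at most 7.0% unadjusted or 8.9% with baseline adjustment. Those figures rest on the assumed 5-15% twitch variation, SD of 4 N, r = 0.7 and one-sided use of the freedom. They show what the rule would allow and do not show that it happened. This is a cheap improvement rather than a flaw that invalidates the trial.

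**What to change.** 1. **Fix the acquisition.** Take five twitches at each peg setting, per leg, at both visits. State that tuning twitches do not count. On day 8, report QuadTw at the angle selected at baseline, before randomization.
2. **Score without the arm.** Keep every tracing under a study and visit code. Have QuadTw computed by an existing team member, or by the monitoring-board member already assigned the statistical analysis, without the arm list. Report the mean of all five twitches as a sensitivity analysis. Re-score the 15 enrolled patients where their tracings are complete, and say plainly that this cannot correct choices made at acquisition.
3. **Separate the roles where existing staffing allows.** For the remaining patients (24 − 15 = 9), have the day-8 and day-28 assessments done by a team member who did not deliver that patient's sessions and has not been told the arm. Swapping staff without the second condition does not mask anyone.

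**Cost:** protocol wording, a short re-scoring task and less freedom in scheduling visits. Carrying the baseline angle forward protects the comparison between arms. It can lower the before-after change within each arm by up to the same 0.25-0.75 N, because the angle was picked for its high baseline value, so the result should be read from the arm difference. Treatment and sample size do not change, and recruitment is paused, so the wording can be settled before the next patient.
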